attitudes regarding dialysis and kidney transplantation. The questionnaire assesses three areas of interest; (1) demographic characteristics and the availability of social and emotional support; (2) self-reported health, quality of life, and the specific impact of kidney disease and its treatment; and (3) patient views of kidney transplantation, including self-reported listing status and perceived bias in transplantation allocation. (4) who patients talk to in the hemodialysis clinic, what they talk about and how often. Many of the items included in the DPTQ have been validated in hemodialysis and transplant populations⁸⁻¹⁵ including quality of life measures and independent predictors of mortality. Previous research has speculated that the social networks that patients form in the hemodialysis clinic may influence attitudes and behaviors towards transplant and may be amenable to social network interventions. Social network behavioral interventions in other fields¹⁶⁻²¹ have found that it may be better to target dense (clustered) networks than diffuse networks. As diffuse networks function as discussion networks and can be more effective in changing behavior than diffuse networks which function as advice networks and are better at spreading novel information through a central person¹⁹⁻²¹. Once patients social networks have been mapped, we will assign every HD clinic shift to one of the two targeting strategies based on social network attributes for the COACH intervention. We will measure the spread of information, attitudes, and behaviors by comparing the targeted patients to those that they refer, as well as the other patients on their shift. The COACH was specifically designed to educate patients on kidney disease and communication skills to approach other people about potential donation.

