Interestingly, 39% of the patients surveyed with the DPTQ reported linking the social aspect of HD. Based on these results, we performed a three-year longitudinal, prospective observational study on the formation of social networks in a new HD clinic and examined the networks' effects on kidney transplantation¹. Forty six racially and ethnically diverse patients (24% White, 33 % Black, 30% Hispanic, and 13% Multiethnic) were enrolled and studied with repeated survey measures and clinical observations. Thirty one patients (67%) were observed interacting with each other and participating in the HD social network (Appendix, Figure2). Gender, not race, was associated with participation in the social network. Almost all (91%) transplant eligible males were linked to other patients compared to 56.3% of the eligible women ($p=0.02$). Patients participating in the social network completed a median of 50% (Interquartile Range (IQR) 33 – 96%) of steps towards transplant compared to a median of 0% (IQR 0 – 23%) of those who did not ($p<0.001$). On sub-network analysis, patients who participated in health discussions with other patients, as well as those who received a kidney transplant had dense, sub-networks with higher clustering coefficients with the a mean of 50% of the patients in their network being interconnected with each other (0.52 ± 0.35 vs. 0.14 ± 0.30 , $p=0.0002$). Women, who participated in the social network, discussed their health more than men (90% vs 45% $p=0.02$) and tended to have a higher clustering coefficient (0.623 vs 0.356 , $p=0.07$). On further sub-network analysis, the percent of the work-up completed by a patient correlated with the steps completed by members of their sub-network ($R^2 = 0.42$, $p = 0.02$) and for patients who were interested but had not started the transplant process (step 2, Table 4), the clustering coefficients predicted the percentage of transplant steps completed ($\beta=2.23$; [95% CI], 0.16-4.29, $p = 0.003$, $r^2=0.19$). Lastly patients, who received a kidney transplant during the study had denser networks (0.71 ± 0.36 vs. 0.23 ± 0.32 , $p= 0.002$). These dense, highly connected networks as measured by the

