patient selected by clustering, will have a clustering coefficient greater than 1 SD from the mean and centrality 1 SD less than a mean. In our previous study, there was no correlation between clustering and centrality ($r=0.024$, $p=0.875$). The research and clinical staff will be blinded to whether the patient was chosen to participate in COACH because of clustering or centrality. Patients will be excluded if they are ineligible for a kidney transplant, had a previous kidney transplant, or have an active living donor.

Assignment of Intervention groups: The intervention assignment will be alternated between MWF and TTS (Table 3) to avoid patient differences between those respective days (for example patients on MWF may have been on dialysis longer while patients on TTS may be more likely to work)⁵⁵.

Retention/Attrition: **AIM3** will be carried out over the course of a year with a possible drop-out rate of 5% (Death and Transfer). If a patient transfers, the patient will be contacted via phone to do a follow-up survey.

Participant Remuneration: All patients will receive \$10 for the initial survey (Wave 1), and Wave 2 survey, \$10 for the 3 month follow-up (Wave 3), and \$10 for Wave 4. Patients will not receive remuneration for participating in the COACH education but will be able to keep the handouts and reading materials.

Data Collection (AIM 3)

Education Intervention: COACH is a behavioral communication intervention designed specifically for ESRD patients pursuing kidney transplantation. The COACH program (appendix) consists of four modules: 1) Kidney transplant options, 2) Discussing your transplant options, 3) Requesting living donation, and 4) Maintaining positive relationships. The content and teaching strategies were guided by the concepts of social cognitive theory as well as principles of adult learning and communication skill acquisition^{31,56,57}. A study coordinator will conduct the intervention in four, face to face, one hour sessions in the HD clinic. Patients will receive the a handbook and video for the COACH intervention.

Shift	Clinic 1		Clinic 2	
	MWF1	TTS1	MWF2	TTS2
1st 5am-9am	Cluster	Central	Central	Cluster
2nd 9am-1pm	Cluster	Central	Central	Cluster
3rd 1pm-5pm	Cluster	Central	Central	Cluster

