Exposure: While only two patients per shift will receive the COACH intervention, all patients regardless of participation in the COACH education will be analyzed as exposed to the intervention via social spread. This will result in two groups for the primary analysis Cluster (MWF1 Cluster + TTS2 Cluster) and Central (MWF2 Central + TTS1 Central)

Analysis: To measure global changes, we will use a t-test to test changes in knowledge and changes in completion of steps between Cluster and Central. Individual level transfer of information will be analyzed with a

Markov chain Monte Carlo accept-reject procedure in the chain⁵⁸. We will examine the correlation in changes of a patient's(ego) knowledge with his or her first degree alter and measure the decay in correlation as the degree of the alter increases. We will also examine the ego's distance (how many links the patients are from each other) from the alter receiving the intervention. In addition, we will use Gaussian Conditional Random Fields (GCRF) methods to model a patient's stage in the transplant process by taking into account various factors such as personal demographics, social influence of alters, and global trends of HD shift and clinic⁵⁹. We will examine the characteristics of the patients disseminate and receive information. The data directly measuring the spread of information, influence, and behavior within the network from this experiment will be used to validate and strengthen the social network model developed in AIM1 and AIM2.

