Limitations: If the targeted patient refuses to participate, we will select another two transplant eligible patients to participate in the intervention based on their clustering and centrality. The network attributes of the patients if they refuse to participate will be analyzed and can inform AIMS 1 and 2 as well as recruitment strategies for future studies. In the unlikely event no patients on the shift participate in the COACH education, they will be analyzed as intention to treat. Since we are measuring change in knowledge using repeated surveys we are at risk for a learning effect⁶⁰. For this reason on the repeated survey questionnaires, we will also assess where the new knowledge came from patient interactions or self-reading after the survey. Given the focus of the proposed research on urban and suburban locales, future research is indicated to see if this social network mapping and intervention can also be used in rural settings, especially since recent studies shown many patients in rural southeast are disadvantaged regarding transplantation⁶¹.

Sample size and power AIM3: Using the data from our previous HD clinic social network study, we expect the patients in the Clustering targeted intervention to complete at least 2 more steps in the transplant work-up than those in the Centrality intervention (7, SD 1.5 vs 5, SD 1.7, p=0.03). The observed effect size was 1.06 or a difference of 2 steps. We estimate at least 10 patients per shift will be exposed to the intervention either directly through participation in the intervention or indirectly through information/behavior spread through the social network. Both clinics have 6 shifts, and we would have 60 patients assigned to each intervention condition. Based on a two tailed t-test, a total sample of 30 (15 in each treatment arm) would yield 80% power at significance level $\alpha = 0.05$ to detect a difference of 2 steps. With 120 patients (60 patients in each treatment arm) we will be powered to detect a difference of 1 step. The COACH intervention produced a change in knowledge³ with an effect size of 1.2, thus if we expose 90 patients (45 in each arm) to the intervention, we will have the power to detect at least half that effect.

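### Cluster or Central is assigned to 12 whole shifts, but the primary t-test and its power count patients as independent; the size and net direction of the error depend on figures the plan does not give

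*SAP*

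**What the plan says.** The unit of assignment is the shift. Protocol section 4 (Rationale & Significance) says "we will assign every HD clinic shift to one of the two targeting strategies". SAP Table 3 (Aim 3, Assignment of Intervention groups) sets out two clinics, two day patterns and three time slots. Clinic 1 MWF and clinic 2 TTS are Cluster; clinic 1 TTS and clinic 2 MWF are Central. That makes six shifts per arm, and the three shifts in any clinic-by-day block share one strategy.

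The unit of analysis is the patient. Under Aim 3, Analysis, the SAP says "we will use a t-test to test changes in knowledge and changes in completion of steps between Cluster and Central". No other test of Cluster against Central is specified.

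The power section (Sample size and power AIM3) makes three statements:
- Two steps: "Based on a two tailed t-test, a total sample of 30 (15 in each treatment arm) would yield 80% power".
- One step: "With 120 patients (60 patients in each treatment arm) we will be powered to detect a difference of 1 step".
- Knowledge, where the full COACH effect is 1.2 SD: "if we expose 90 patients (45 in each arm) to the intervention, we will have the power to detect at least half that effect".

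None of them mentions an ICC, a design effect or the number of shifts as a limit on information.

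Dependence is recognised elsewhere. The Preliminary Results report that "the percent of the work-up completed by a patient correlated with the steps completed by members of their sub-network" (R² = 0.42). The Aim 1 analysis plans a bootstrap because observations are not independent. Aim 3 lists shift and clinic as covariates and describes a Gaussian conditional random field model with shift and clinic trends. None of these enters the t-test.

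**The concern.** When whole shifts receive a strategy, the difference between arms varies with the shifts as well as with the patients in them. A patient-level t-test sees only the patients. If shifts differ for reasons beyond clinic, day pattern and time slot, its standard error is too small for that source of variation.

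In this trial the dependence is part of the hypothesis. Two educated patients are meant to influence everyone else on their shift, so success or failure of spread on a given shift moves its patients together.

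Two things are at stake. A chance difference between shifts could be read as an advantage of one targeting strategy and carried into the national study that the SAP names as the next step. And the stated ability to detect one step, or half the COACH knowledge effect, depends on an ICC that the plan never states.

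**Working it through.** **Inputs from the documents.** 12 shifts, 6 per arm (Table 3). At least 10 patients per shift, so 60 per arm (power section). Steps 7 (SD 1.5) v 5 (SD 1.7), stated effect size 1.06. Knowledge d = 1.2/2 = 0.6. Expected enrolment 252, so 252/12 = 21 per shift if everyone is analysed (Aim 3, Exposure). Two-sided alpha 0.05.

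**Assumed.** Every ICC value. Two SDs are carried because the printed figures give √((1.5² + 1.7²)/2) = 1.60, while 2/1.06 = 1.89. Both are taken to apply to change in steps.

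**1. Reproducing the plan (independent patients, noncentral t).** 15 per arm, d = 1.06: 0.800. 60 per arm, d = 0.53: 0.821. 45 per arm, d = 0.6: 0.804. The arithmetic is right, given independence.

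**2. Type I error if the whole ICC is residual shift variation.** With m patients per shift, design effect DE = 1 + (m − 1)·ICC, and type I error ≈ 2·[1 − Φ(1.96/√DE)].

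| ICC | DE, m = 10 | Error | DE, m = 21 | Error |
|---|---|---|---|---|
| 0.01 | 1.09 | 6% | 1.20 | 7% |
| 0.02 | 1.18 | 7% | 1.40 | 10% |
| 0.05 | 1.45 | 10% | 2.00 | 17% |
| 0.10 | 1.90 | 16% | 3.00 | 26% |

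Simulation on the Table 3 layout agrees with these to the rounding shown.

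**3. The opposing force.** Each arm has three shifts per clinic, three per day pattern and two per time slot. Main effects of these cancel from the difference between arms but stay in the t-test's error variance, which makes the test conservative. Suppose change differs by 1 SD between clinics (assumed). Half of each arm is in each clinic, so the error variance gains 1²/4 = 0.25, and type I error ≈ 2·[1 − Φ(1.96·√(1.25/DE))]. With 10 per shift and ICC 0.01, 0.02, 0.05, 0.10 this gives about 3.5, 4.3, 7 and 11%, as does simulation. Under that assumption the two forces balance where DE = 1.25, at ICC = 0.25/9 = 0.028.

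**4. Power on 12 shifts.** Shift-level t-test with 10 df and noncentrality d·√(6m/(2·DE)), assuming no block variance.

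| Contrast | ICC 0 | 0.05 | 0.10 |
|---|---|---|---|
| 1 step, 60 per arm, SD 1.60 | 0.87 | 0.73 | 0.61 |
| 1 step, 60 per arm, SD 1.89 | 0.74 | 0.59 | 0.48 |
| Knowledge 0.6 SD, 45 per arm | 0.73 | 0.61 | 0.52 |
| Knowledge 0.6 SD, 60 per arm | 0.84 | 0.69 | 0.58 |

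With 21 per shift and the full 1-step effect, power at ICC 0.05 is 0.88 (SD 1.60) or 0.76 (SD 1.89). The 2-step contrast at 60 per arm is 0.86 or more up to ICC 0.20, for either SD and with 8 or 10 df.

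**5. Block structure.** The contrast is (clinic 1 MWF + clinic 2 TTS) − (clinic 1 TTS + clinic 2 MWF), which is the clinic-by-day interaction. With an assumed block ICC of 0.02 and shift ICC of 0.05, even a shift-level test has simulated type I error of about 8 to 11%.

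**The case against.** The best defence is the layout. Table 3 balances clinic, day pattern and time slot, and the SAP describes two very different clinics (94% v 37% African American; median income $28,363 v $82,406). A large clinic difference left in the error term could outweigh a small shift ICC. This stands: step 3 shows error below 5% at ICC 0.01 and 0.02 under a 1 SD clinic difference. It does not rescue the test, because the offset depends on an unplanned and unknown quantity and fails at larger ICCs.

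It can also be said that the effect the plan expects, at least 2 steps with 60 per arm, survives clustering. That is correct. The 45-per-arm knowledge figure is conditional in the SAP, and the 60 per arm expected there does better. Also correct, and both are shown.

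The 21-per-shift figures rest on one of two readings. The Aim 3 Recruitment Goals and Exposure text count every patient on the shift, while the power section uses at least 10 and the Aim 3 recruitment text lists exclusions that may apply only to COACH targets.

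The covariate list and the random field model are a weaker defence. A two-sample t-test takes no covariates, and no strategy contrast is specified from the model.

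Finally, the SAP calls this a pilot. It nonetheless states a directional hypothesis, primary outcomes and 80% power.

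**Conclusion.** The mismatch between unit of assignment and unit of analysis is real and affects the only stated test of the primary contrast. It should be corrected before analysis. Its size is conditional: about 6 to 16% type I error with 10 per shift, or 7 to 26% with 21, for assumed ICCs of 0.01 to 0.10 that are wholly residual shift variation, and less where balanced clinic, day or slot differences are large. The 1-step and knowledge power statements are sensitive to the ICC; the 2-step contrast at 60 per arm is not.

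Three stronger readings are tempting and are not supported:
- That type I error must exceed 5%. Step 3 shows that even the direction depends on unstated quantities.
- That R² = 0.42 is the shift ICC. It is a correlation among sub-network members in an earlier study; it supports positive dependence but does not measure it by shift.
- That the study is underpowered outright. Power for 1 step ranges from adequate to poor with the ICC, the SD and the number analysed per shift.

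**What to change.** 1. For both steps and knowledge, replace the t-test with a linear mixed model: random effect for the 12 shifts, small-sample degrees of freedom, and fixed effects for strategy, baseline value, clinic and day pattern. Alternatively, compare the 12 shift means adjusted for clinic and day (12 − 4 = 8 df). Do not enter the 12 shifts as fixed effects, because they are aliased with strategy.

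2. Restate power as the difference detectable with 80% power over a stated ICC range on 12 shifts. For ICC 0.01 to 0.20 and 8 df:
   - steps, 10 per shift: about 0.98 to 1.6 (SD 1.60) or 1.15 to 1.85 (SD 1.89);
   - knowledge: 0.70 to 1.02 SD at 45 per arm, or 0.61 to 0.98 SD at 60 per arm, against the planned 0.6.

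3. State which patients on each shift are analysed, and use that count in both the power and the analysis text.

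4. State as a limitation that strategy coincides with the clinic-by-day interaction over four blocks. No model separates the two, and the new test does not secure 5% if blocks vary.

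The cost is SAP wording only, with no new patients or data. The price is a less favourable power statement and an open limit on attributing a difference to strategy. The gap between the stated effect size of 1.06 and the 2/1.60 = 1.25 implied by the printed means and SDs is a separate minor point.

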- v. We propose a pre-post design to assess the impact of the COACH education on patients' transplant-related knowledge and behaviors. Before administering the COACH education, we will survey targeted patients to assess changes in knowledge and behaviors towards transplant from the baseline survey. As another measure of the impact of the COACH intervention, patients not receiving the intervention will serve as controls and will be surveyed along with those receiving the intervention; we will then assess within and between group differences in transplant-related knowledge and behaviors. To assess the dissemination of information contained in the COACH intervention, all patients will be surveyed at 3-months post-intervention. The follow-up surveys will determine the sources of these changes (eg. self-reading after the survey, the COACH intervention, or discussing with other patients). Finally, during Year 4, one year post-intervention, a final survey will be administered to all the patients in both clinics to assess retention of information and change in attitudes and behaviors of those who participated in COACH and the spread of information and behaviors to the patients who were not targeted.
- vi. The medical information collected is age, insurance status, ESRD diagnosis, vascular access. Medical comorbidities: congestive heart failure, peripheral vascular disease, malignancy. Mental Health, Substance Abuse, and HIV information is not collected. If the patient has ESRD from HIV the diagnosis is coded as glomerulonephritis a common and non-specific cause of ESRD.

Phosphate binding medication, Vitamin-D, and Calcimetic prescribing information is collected. Laboratory data includes basic metabolic panel, phosphorus, cbc, iron studies, hepatic function, cholesterol. Data collected will be analyzed to better understand barriers to transplantation and compare self-reported (survey) health data to laboratory data. All data is entered in an Excel spreadsheet and analyzed in SPSS 17.0, using descriptive statistics, chi-square test of association and t-tests. Time series analysis will be done in MathWorks MATLAB software. A p-value of less than 0.05 will be deemed significant.

- e. **Withdrawal of Subjects:** Patients may withdraw at anytime, this will be as a result of the patient transferring out of the clinic. Once, the patient withdraws they can contact the survey researcher or the PI and data will stop being collected.

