Survey Instrument: The *Dialysis Patient Transplant Questionnaire* (DPTQ) includes a mix of 49 questions, single measures, and scales previously validated in HD and transplant populations and items developed to address the co-investigators' specific research interests (see appendix). The DPTQ has demonstrated construct validity in previous studies^{1,4,11,12}. It includes 17 items on communication confidence developed specifically to evaluate the COACH program and rated along a scale from 0 to 100 (Cronbach's alpha = .90); summed to create a composite confidence score. In addition, there are 12 true/false items on transplant knowledge items; correctly answered items are summed to create a composite knowledge score. The questionnaire will also include questions regarding medical conditions which may preclude the patient from transplantation. Clinic staff will also participate in a modified version of the survey to assess their attitudes towards HD^{48,49} and kidney transplantation, during Year 2.

Participant HD Seating and Observed Interaction Log: Patient seating assignments will be recorded, as well as, the staff observed social interaction log, which documents the frequency, duration, and nature of observed patient-patient interactions (appendix).

Clinical Data: Upon consent, routine HD laboratory and clinical data (including co-morbid conditions, e.g. diabetes, congestive heart failure, cardiovascular disease, chronic obstructive pulmonary disease, and malignancy, which will be reconciled with survey data) will be extracted from the DARWIN database by the DCI Information Technology Department. Data will be downloaded, cleaned, merged, and submitted for preliminary analysis. Patient's steps to transplantation (Table 2)^{1,2} will be recorded and listing status will be verified with the patient transplant center or centers (**AIM 2**).

Analytic Plan AIM1: To test **H1**, we will create nodal network graphs (Figure 1, for example) using data collected from the patient and staff surveys, and clinical observations. We will characterize and compare the structure of the patient HD clinic networks by gender and race. We will assign demographic, survey, and clinical data abstracted from the EMR to each node in the network.

Primary outcome: Differences in clustering and centrality by gender and race (**H1**)

Independent Variables: Sex and Race

Covariates: Age, Marital Status, HD vintage, insurance, HD Clinic, and HD shift

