Staggered Surveys: We propose a pre-post design to assess the impact of the COACH education on patients' transplant-related knowledge and behaviors. Before administering the COACH education, we will survey targeted patients to assess changes in knowledge and behaviors towards transplant from the baseline survey. As another measure of the impact of the COACH intervention, patients not receiving the intervention will serve as controls and will be surveyed along with those receiving the intervention; we will then assess within and between group differences in transplant-related knowledge and behaviors. To assess the dissemination of information contained in the COACH intervention, all patients will be surveyed at 3-months post-intervention. The follow-up surveys will determine the sources of these changes (eg. self-reading after the survey, the COACH intervention, or discussing with other patients). Finally, during Year 4, one year post-intervention, a final survey will be administered to the all the patients in both clinics to assess retention of information and change in attitudes and behaviors of those who participated in COACH and the spread of information and behaviors to the patients who were not targeted.

Clinical Data: In addition to the survey data, we will collect patient transplant listing status, living donor evaluations from participants' respective transplant centers.

Analytic plan AIM3: To test **H3** we will assess the successful spread of the intervention by evaluating the difference in the primary outcome of completion of steps toward transplantation between patients being exposed via the most clustered (Cluster) members versus the most central (Central). We will use repeated surveys to measure our secondary outcomes include change in knowledge, attitudes, behaviors of the patients either directly exposed to the intervention or those who were exposed indirectly through the social network.

Primary Outcomes: 1) Differences in patient knowledge, 2) Differences in transplant steps completed

Secondary Outcomes: 1) Completion of transplant work-up, 2) Asking for a living donor

Independent Variables: Intervention assignment to Cluster or Central

Covariates: Age, Marital Status, insurance, transplant eligibility, HD shift, HD Clinic, network attributes

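### The primary Cluster v Central t-test on change scores uses baseline only by subtraction and none of the listed covariates, so it gives up precision and leaves patient-level imbalance unadjusted

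*SAP*

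**What the plan says.** The Aim 3 analysis paragraph of the SAP sets the between-arm comparison in one sentence: "we will use a t-test to test changes in knowledge and changes in completion of steps between Cluster and Central". The outcomes are given as "Primary Outcomes: 1) Differences in patient knowledge, 2) Differences in transplant steps completed". Just below that, the SAP has "Covariates: Age, Marital Status, insurance, transplant eligibility, HD shift, HD Clinic, network attributes". Baseline step and baseline knowledge are not on that list, although both are collected: steps are recorded under Aims 1 and 2, where "listing status will be verified with the patient transplant center or centers", and the knowledge score comes from the baseline questionnaire.

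One further Aim 3 model uses patient characteristics. The Gaussian Conditional Random Field model describes transplant stage "by taking into account various factors such as personal demographics, social influence of alters, and global trends of HD shift and clinic". It is an added analysis, covers stage only, and states no Cluster v Central contrast. The protocol's data analysis section adds only descriptive statistics, chi-square tests, t-tests and time series, with "A p-value of less than 0.05 will be deemed significant". The sample size is likewise "Based on a two tailed t-test".

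On assignment, the SAP says: "The intervention assignment will be alternated between MWF and TTS (Table 3) to avoid patient differences between those respective days". No randomisation of shifts is described.

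**The concern.** The plan names covariates and then specifies a primary test that cannot use them. By contrast, Aims 1 and 2 specify regression models.

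Two things are at stake. The first is precision. Starting position is likely to matter for progress: on the eight-step scale a patient at step 7 can gain only one step, and all patients on a shift are analysed as exposed, whether or not they are transplant candidates. The power paragraph expects a mean of 7 (SD 1.5) in the Cluster arm. If that is an attained step, the mean lies (8 − 7)/1.5 = 0.67 SD below the top of the scale.

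The second is imbalance between the arms in characteristics other than the baseline outcome, for which the primary test makes no adjustment.

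**Working it through.** **Inputs.** From the SAP's Aim 3 sample size paragraph: two-sided α = 0.05; effect size 1.06 for 2 steps, so SD = 2/1.06 = 1.887; 15 or 60 patients per arm for steps; 45 per arm for half of a knowledge effect of 1.2. From the Aim 3 retention paragraph: 5% drop-out. From Table 3: 12 shifts. The baseline-to-follow-up correlation ρ, the ratio k of follow-up to baseline SD, and the intra-shift correlation (ICC) are not in the documents. All values used for them are assumptions.

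**The plan's own figures.** The exact noncentral-t calculation gives:
- d = 1.06, 15 per arm: 80.0% power.
- 1 step, SD 1.887, 60 per arm: 82.1%, and 80.1% with 57 per arm after 5% drop-out.
- Knowledge, d = 0.6, 45 per arm: 80.4%.

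The stated sizes reproduce. The quoted means and SDs would give a pooled SD of 1.603 and d = 2/1.603 = 1.25, so using 1.06 is the cautious choice.

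**Precision, equal variances.** Var(change) = 2·SD²·(1 − ρ). The residual variance after regression on baseline is SD²·(1 − ρ²). The ratio is (1 + ρ)/2. The SAP does not say whether 1.887 is the SD of change. If it is, then for 1 step at 60 per arm, with patients treated as independent as in the SAP:

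| ρ (assumed) | Variance ratio | Power, t-test on change | Power, baseline-adjusted | n per arm for 80% (t-test: 57) |
|---|---|---|---|---|
| 0.3 | 0.65 | 82.1% | 94.6% | 38 |
| 0.5 | 0.75 | 82.1% | 91.4% | 43 |
| 0.7 | 0.85 | 82.1% | 87.8% | 49 |
| 0.9 | 0.95 | 82.1% | 84.0% | 55 |

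If 1.887 is instead the SD at a single time, change score v baseline-adjusted power is 68.2% v 85.5% (ρ = 0.3), 82.1% v 91.4% (0.5) and 96.1% v 98.1% (0.7).

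**Precision, unequal variances.** With baseline variance set to 1, Var(change) = 1 + k² − 2ρk and the adjusted variance is k²(1 − ρ²). The difference is (1 − ρk)².
- ρ = 0.5, k = 1.5: 1.6875/1.75 = 0.96, against 0.75 at k = 1.
- ρ = 0.8, k = 1.25: 0.5625/0.5625 = 1, so no saving.

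**If the arms differ at baseline.** With equal variances, the two estimates differ by (1 − ρ) step for each step of baseline difference. For a hypothetical 1-step difference this is 0.7, 0.5, 0.3 and 0.1 step at ρ = 0.3, 0.5, 0.7 and 0.9. The trial is sized to detect 1 step.

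**What Table 3 balances.** Each arm has three shifts from each clinic, three from each day pattern and two from each time slot. But Cluster is MWF in Clinic 1 and TTS in Clinic 2, and Central is the reverse, so arm is the clinic-by-day interaction. Day differences cancel only if they are the same in both clinics. The SAP itself suggests that the day patterns may differ in time on dialysis and in employment, and it describes clinics that differ widely in race and income.

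**Allowing for shift.** With 10 patients per shift, the design effect is 1 + 9·ICC, and 12 shifts in two arms leave 10 degrees of freedom. Unadjusted power for 1 step is then about 74% at ICC 0, 59% at 0.05 and 48% at 0.10.

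**The case against.** A reader might infer that the test ignores the starting step and leaves baseline imbalance wholly uncorrected. It does not: analysing changes subtracts each patient's baseline. The limitation is the fixed slope of 1, which over-corrects when the true slope is lower.

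A reader might also infer that an arm starting lower will show spurious progress. The documents do not support this. The (1 − ρ) gap measures disagreement between two methods. It is the error of the change score only if both arms regress towards a common mean. Without randomisation, a stable difference between the groups could make the baseline-adjusted estimate the biased one. The SAP also says that the main barrier is finishing the work-up, so steps are not equally easy and a lower start need not mean more progress. Verification of listing status limits regression to the mean from reporting error.

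Other objections stand in part. Table 3 does balance clinic, day pattern and time slot, so omitting those costs mainly precision. The Gaussian model uses some covariates, but without a contrast between arms. This is described as a pilot, and its stated power reproduces. Finally, the precision gains above treat patients as independent, whereas proper allowance for shift works the other way.

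**Conclusion.** The point holds as one of efficiency and unadjusted covariates. The primary comparison uses none of the seven listed covariates and handles baseline only by subtraction. Under assumed correlations of 0.3 to 0.9 and equal variances, it gives up 35% to 5% of variance relative to baseline adjustment. The saving falls to about 4% at ρ = 0.5 with an SD ratio of 1.5, and to nothing where ρk = 1. No single figure can be fixed from the documents.

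Imbalance in age, marital status, insurance and transplant eligibility is possible, not shown. A 1-step baseline difference is hypothetical, and neither method is guaranteed unbiased under this assignment. Covariate adjustment alone would not make the test valid, because patients are nested in 12 shifts and linked by their networks. The Aim 1 analysis recognises this dependence; the Aim 3 t-test does not.

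**What to change.** Pre-specify as primary, for steps and for knowledge, a regression of the follow-up value at one named wave on arm, the pre-intervention (Wave 2) value, clinic, age, marital status and insurance. Add transplant eligibility if ineligible patients are analysed; the SAP's exposure paragraph suggests they are, while its power count covers eligible patients only. Include a shift-level random effect, with small-sample degrees of freedom for 12 shifts. The SAP does not say which waves define the change, so the follow-up wave must be stated in any case. Report the change-score t-test as a sensitivity analysis, so that any disagreement between the methods is visible.

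This is a cheap improvement: SAP wording and a little more analysis, using variables already planned for collection. It is not wholly free. Allowing for shift will give wider intervals than the independent-patient t-test assumed in the sample size paragraph. The net effect on power depends on the correlation and the ICC, neither of which the documents give. The clinic-by-day interaction cannot be adjusted for, because it is identical to arm; patient-level covariates are the only protection on that side.
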